9.4 Third Therapy

All patients completing cycle 12 with bosutinib plus atezolizumab therapy will continue with bosutinib 400 mg/day in monotherapy for 12 more cycles.

9.5 Withdrawal criteria

Patients may suspend their participation in the study whenever they wish, based on his/her own judgement and opinion, without giving any explanation, although the investigator may investigate the reasons of a voluntary dropout.

The investigator may also decide to withdraw a patient from the trial if he/she does not comply with the protocol, due to AEs or treatment inefficacy or toxicity.

Patients who do not comply with at least 70% of the scheduled doses of bosutinib or that, in 4 or more times, the administration of atezolizumab is cancelled, will be withdrawn from the study.

10 POPULATION

10.1 Patient Population

The target population of this study includes naïve adult patients of both genders with chronic myeloid leukemia in chronic phase.

10.2 Inclusion Criteria

Patients eligible for inclusion in this study have fulfill the following criteria:

1. Male or female patient \geq 18 years of age.
2. Evidence of a personally signed and dated informed consent document indicating that the patient (or a legal representative) has been informed of all pertinent aspects of the study.
3. Patients who are willing and able to comply with scheduled visits, treatment plan, laboratory tests, and other study procedures
4. Newly Patient with Philadelphia chromosome positive chronic phase CML and BCR-ABL1 transcript detected at diagnosis.
5. ECOG Performance Status of 0, 1, or 2.
6. Adequate hepatic, renal and pancreatic function defined as:
 - a. Total bilirubin within normal range or Direct bilirubin \leq 1.5 x ULN,
 - b. Aspartate aminotransferase (AST)/Alanine aminotransferase (ALT) \leq 2.5 x upper limit of normal (ULN) or \leq 5 x ULN if attributable to liver involvement of leukemia,
7. Have a negative pregnancy test documented prior to enrollment (for females of childbearing potential). A woman is considered of childbearing potential, i.e. fertile, following menarche and until becoming post-menopausal unless permanently sterile. Permanent sterilisation methods include hysterectomy, bilateral salpingectomy and bilateral oophorectomy (CTFG, 21/09/2020). These women, must have a negative serum or urine pregnancy test before initiation of study treatment and must also use highly effective methods of contraception while enrolled in the study. The use of highly effective contraception should continue for at least 14 days after the last dose of study treatment. Acceptable forms of highly effective contraception methods include (CTFG, 21/09/2020):
 - a. Total abstinence [when this is in line with the preferred and usual lifestyle of the patient. Periodic abstinence (e.g., calendar, ovulation, symptothermal, post-ovulation methods) and withdrawal are not acceptable methods of contraception]
 - b. Male/female sterilization. These defined as:
 - Female sterilization (have had surgical bilateral oophorectomy with or without hysterectomy) or tubal ligation at least six weeks before taking study treatment.
In case of oophorectomy alone, only when the reproductive status of the woman has been confirmed and documented by follow-up hormone level assessment.

- Male sterilization (at least 6 months prior to screening). For female patients on the study, study participation assumes the vasectomized male partner is the sole partner for that patient.

c. Contraceptive methods:

- i. Combined (estrogen and progestogen containing) hormonal contraception associated with inhibition of ovulation: oral, intravaginal or transdermal.
- ii. Progestogen-only hormonal contraception associated with inhibition of ovulation: oral, injectable or implantable.
- iii. Placement of an intrauterine device (IUD) or intrauterine system (IUS).

Women are considered post-menopausal and not of child bearing potential if they have had 12 months of natural (spontaneous) amenorrhea with an appropriate clinical profile (e.g., age appropriate, history of vasomotor symptoms) or have had surgical bilateral oophorectomy with or without hysterectomy or tubal ligation at least six weeks prior to enrolling. In the case of oophorectomy alone, only when the reproductive status of the woman has been confirmed by follow-up hormone level assessment is she considered not of child bearing potential.

If a study patient gets pregnant or is suspected of being pregnant during the study or within 30 days as part of safety evaluations after the final dose of bosutinib, the study Doctor needs to be informed immediately and any ongoing study treatment with bosutinib has to be stopped immediately.

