- after prior platinum containing chemotherapy, or
- who are considered cisplatin ineligible, and whose tumours have a PD-L1 expression ≥ 5%.

Also, in combination with bevacizumab, paclitaxel and carboplatin, atezolizumab is indicated for the first-line treatment of adult patients with metastatic non-squamous non small cell lung cancer (NSCLC). In patients with EGFR mutant or ALK-positive NSCLC, atezolizumab, in

combination with bevacizumab, paclitaxel and carboplatin, is indicated only after failure of appropriate targeted therapies.

Atezolizumab as monotherapy is indicated for the treatment of adult patients with locally advanced or metastatic NSCLC after prior chemotherapy. Patients with EGFR mutant or ALK positive NSCLC should also have received targeted therapy before receiving atezolizumab.

Atezolizumab at a dose of 1–20 mg/kg produced a dose-proportional increase in exposure to the drug. Typical clearance was 0.20 L/day, volume of distribution at steady state was 6.9 L, and the terminal half-life was 27 days, according to a population analysis of patients in the dose range (n = 472). This population analysis also suggested steady state occurs after 6–9 weeks treatment (2–3 dosage cycles). Systemic accumulation in terms of area under the plasma concentration time curve (AUC), maximum concentration (C_{max}) and trough concentration (C_{min}) was 1.91, 1.46 and 2.75-fold, respectively. The systemic exposure to atezolizumab was not significantly affected when analysed according to patient age, body-weight, gender, positive anti-therapeutic antibody status, albumin levels, tumour burden, region or race, mild or moderate renal impairment, mild hepatic impairment, level of PD-L1 expression, or Eastern Cooperative Oncology Group (ECOG) performance status. The potential for atezolizumab to interact with other drugs is unknown (*Markham, 2016; EMA, 2019*).

Major common AEs involved fatigue, decreased appetite, nausea, diarrhea, pyrexia, pruritus, cough, edema peripheral, and rash. The most common severe AEs were fatigue, anemia, and dyspnea. The overall atezolizumab-related death rate was much lower than chemotherapeutics-related death rate. Atezolizumab has better overall survival and lower risk of AEs compared with chemotherapy (*Tie, 2019*).

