12 VISIT SCHEDULE AND ASSESSMENTS

12.1 Schedule of Events

Details on scheduling and sample collection are described in Tables 14-17. The tables 14 and 15 for 1st group of patients (first 10 patients included), and the tables 16 and 17 for 2nd group of patients (the last 26 patients included).

All data obtained from these assessments must be recorded in the source documentation. The CRF will not be used as a source document for any study data.

Please maintain a special awareness of the assessments of the primary and secondary endpoints.

All visits should be completed on the designated day or as close as possible. However, the windows allowed by protocol will be:

- For visits that take place every two weeks, the window will be ± 3 days.
- For visits that take place every 4 weeks, the window will be ± 3 days.
- For visits that take place every 3 cycles (every 12 weeks), and the End of Treatment visit, the window allowed will be ± 14 days.

For this purpose, a cycle equal to 28 days (4 weeks) will be defined and one month will be considered to be equivalent to one cycle.

Table 14. Schedule of Assessments 1st and 2nd Therapies for the First 10 Patients

The following visit schedule will apply if the atezolizumab dose does not need to be adjusted during 2nd therapy due to DLTs. If the dose of atezolizumab has to be modified to the 840 mg every two weeks, additional visits will be scheduled for the administration of atezolizumab. The only procedure to be conducted during these additional visits is the administration of atezolizumab

1 st Group of Patients (The 10 First Patients)		1 st Therapy		2 nd Therapy													
VISIT	Visit 0	Visit 1	Visit 2	Visit 3	Visit 4	Visit 5	Visit 6	Visit 7	Visit 8	Visit 9	Visit 10	Visit 11	Visit 12	Visit 13	Visit 14	Visit 15	Visit 16
Cycle	Screening / Baseline	Cycle 1		Cycle 2		Cycle 3		Cycle 4	Cycle 5	Cycle 6	Cycle 7	Cycle 8	Cycle 9	Cycle 10	Cycle 11	Cycle 12	Cycle 13
Day within Cycle (Visit Window ± 3 Days)	-28/-1	1	15	1	15	1	15	1	1	1	1	1	1	1	1	1	1
Consecutive Days in the Study (D)	-28/-1	D1	D15	D29	D43	D57	D71	D85	D113	D141	D169	D197	D225	D253	D281	D309	D337
Informed Consent	X																
Eligibility	X	X ⁽¹⁾															
Inclusion/Exclusion Criteria (Checklist)	X	X ⁽¹⁾															
Medical/Surgical History and Demographics	X																
Recent Medication Prior to First Dose of IMP	X	X ⁽¹⁾															
Leukemia Diagnosis and Prior Cancer Therapy	X																
Sokal Risk Score	X																

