12.17 Pregnancy Test

The pregnancy test must be a beta-human chorionic gonadotropin (β -HCG) test, using either urine or serum. Women who are not of childbearing potential (status post- hysterectomy, status post-bilateral oophorectomy, or postmenopausal [defined as amenorrhea for at least 12 months]) do not need to have the test performed. If the test is deemed necessary, it must be performed in screening visit or during visit 1 before the first dose of study drug and known to be negative prior to drug administration. Women of childbearing potential at study start must also complete the pregnancy test each month during the study, at the end-of-treatment visit and at the end-of-study visit.

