13.14 Contraception and Pregnancy

Females of childbearing potential and fertile males will be informed of the potential risk of conception while participating in this study. Females of childbearing potential are required to use a highly effective form of contraception from recruitment through at least 4 months after the end of treatment (see inclusion criterion 7)

A pregnancy test will be performed on each premenopausal female of childbearing potential within 7 days prior to first dose of bosutinib, and again each month during the study, at the end-of-treatment visit and at the end-of-study visit. A negative pregnancy test must be documented prior to administration of study drug.

Females should be advised to take a pregnancy test if their period is late, and to inform their investigator of the result.

If a patient is confirmed pregnant during the trial, study drug administration must be discontinued immediately. The investigator must also immediately notify the sponsor medical monitor of this event and record the pregnancy on a pregnancy form. Initial information regarding a pregnancy must be immediately (in less than 24 hours) forwarded to FTH Pharmacovigilance and Risk Management or its designated representative.

The investigator must immediately report follow-up information to the sponsor regarding the course of the pregnancy, including perinatal and neonatal outcomes, regardless of whether the patient has discontinued participation in the study. If the pregnancy results in the birth of a child, additional follow-up information may be requested. If the pregnancy results in spontaneous abortion or stillbirth, that event should be reported as a SAE.

Pregnancy outcomes must also be collected for the female partners of any males who took study drug in this trial. Consent to report information regarding these pregnancy outcomes should be obtained from the female partner.

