14 CO-TREATMENT AND TREATMENT SUPPLY

14.1 Prior and Concomitant Treatment

All concomitant medications administered from the time of informed consent signature until 28 days after end of treatment (either the last dose of study drug or the investigator/patient decision to discontinue, whichever occurs later), are to be recorded in the patient's eCRF.

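### Inclusion criterion 7 requires contraception for 14 days after the last dose; Protocol Section 13.14 requires 4 months after end of treatment and cites criterion 7 for it

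*Protocol*

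**What the plan says.** Two operative sections of the protocol set a post-treatment minimum for women of childbearing potential.

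- **Protocol Section 10.2, criterion 7:** "The use of highly effective contraception should continue for at least 14 days after the last dose of study treatment". The sentence before it requires highly effective contraception throughout enrolment. SAP Section 5.2 repeats the criterion with the same period.
- **Protocol Section 13.14:** women must use a "highly effective form of contraception from recruitment through at least 4 months after the end of treatment (see inclusion criterion 7").

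Criterion 7 gives no 4-month period anywhere. The synopsis version of the criterion gives no duration.

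The related safeguards are these:

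- Section 12.17 schedules pregnancy tests monthly and "at the end-of-treatment visit and at the end-of-study visit". Tables 15 and 17 place the end-of-study visit 28 days after the last dose.
- Criterion 7 asks for immediate notice of a pregnancy during the study or "within 30 days as part of safety evaluations after the final dose of bosutinib".
- Section 13.14 adds: "Females should be advised to take a pregnancy test if their period is late", with no stated end date. It also requires pregnancies to be followed up.

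**The concern.** Both sentences are current text and cover the same women, but their minimums differ roughly eightfold. The cross-reference makes this worse: a reader who follows Section 13.14 back to its cited source finds the shorter figure. Eligibility is checked against criterion 7, so 14 days is the number a site is likely to have in front of it.

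At stake is when a woman is told she may stop contraception. The scheduled tests and the notice rule detect a pregnancy; they do not prevent one. They also lapse about a month after the last dose, well before Section 13.14's period ends.

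**Working it through.** There is no sample-size or power figure to reproduce. The check compares the two rules and counts days.

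**Inputs**

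- Criterion 7: 14 days after the last dose, or to the end-of-study visit (day 28 after the last dose) for a woman still enrolled then.
- Section 13.14: 4 months after the end of treatment.
- Length of a month: Section 12.1 says "one month will be considered to be equivalent to one cycle", that is 28 days. The convention is given for visit scheduling, so calendar months are shown as well.

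**Length of 4 months**

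- Protocol convention: 4 × 28 = 112 days.
- Calendar: 4 × 365.25/12 ≈ 122 days.

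**Shortfall of criterion 7 against Section 13.14**

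| Relying on | 28-day months | Calendar months |
|---|---|---|
| 14 days after the last dose | 112 − 14 = 98 days | 122 − 14 = 108 days |
| Enrolment to the end-of-study visit | 112 − 28 = 84 days | 122 − 28 = 94 days |

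The last scheduled pregnancy test is also at day 28, so the same 84 to 94 days follow it. After the 30-day notice period, 112 − 30 = 82 to 122 − 30 = 92 days remain.

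**Can the different starting points explain the gap?** No. For completers, Section 12.9 makes the end-of-treatment visit the day of the last dose, so the two coincide. For early stoppers, Section 12.20 places the termination visit within 14 days of the last dose or of the decision to stop. Section 14.1, on concomitant medication, describes "end of treatment (either the last dose of study drug or the investigator/patient decision to discontinue, whichever occurs later"). If that reading carries over, Section 13.14's period can only start at the last dose or later, which widens the gap. Section 11.6 allows up to one month off bosutinib, so a woman held off both drugs and then withdrawn could have a decision date up to about a month after her last dose.

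**Context only: residual atezolizumab.** Section 6.3 gives: "Typical clearance was 0.20 L/day, volume of distribution at steady state was 6.9 L, and the terminal half-life was 27 days". With single-exponential decay the fraction left t days after an infusion is 2^(−t/27). For a woman who stops treatment 0 to 28 days after an infusion:

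- 14 days after stopping: 2^(−14/27) = 0.70 to 2^(−42/27) = 0.34.
- 28 days after stopping: 2^(−28/27) = 0.49 to 2^(−56/27) = 0.24.
- 4 months after stopping: 2^(−112/27) = 0.056 to 2^(−150/27) = 0.021.

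For a completer, with the last infusion on D337 and the last bosutinib dose on D700, the fraction at D714 is 2^(−377/27) ≈ 0.00006. The documents link none of these levels to fetal risk, so they do not show which period is correct.

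**The case against.** The strongest reply is that no duty is missing. Both periods are minimums, 4 months meets both, and it stands in the section devoted to contraception, which also requires that women be informed of the risk. Harm needs a site to apply criterion 7 and overlook Section 13.14. The patient information was not available for review and may already say 4 months. All of this stands, and it limits the seriousness. It does not remove the defect, because Section 13.14 itself points to criterion 7.

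A second reply is that criterion 7 also binds women throughout enrolment, so 14 days is not its full reach. This stands too, for women who stay to the end-of-study visit; the 84 to 94 day figure reflects it.

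A reader might infer that 14 days was meant for bosutinib and 4 months for atezolizumab, so that only women stopping during or soon after the combination phase are affected and completers are not. The half-life figures make this tempting, but no section assigns either period to a drug. Section 13.14 counts from the end of treatment for every woman of childbearing potential, including those who finish the last 12 cycles on bosutinib alone.

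**Conclusion.** The inconsistency is real and should be corrected. By the protocol's own stricter rule, criterion 7 is too short by about 98 to 108 days, or about 84 to 94 days for a woman who remains enrolled to the end-of-study visit. The ranges rest only on whether a month is 28 days or a calendar month, and on the end of treatment coinciding with the last dose; a later decision to discontinue lengthens them.

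The number of women affected is not known. They are an uncounted part of the 36 planned patients of both sexes, completers included.

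A reader might go further and conclude that the protocol lacks adequate contraceptive protection, or that 4 months has been shown to be the right period. The documents support neither: the longer duty is already stated, and they do not say which of the two figures was intended. Confidence is high that the texts conflict. Choosing 4 months is the cautious resolution and needs the sponsor's confirmation.

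**What to change.** In criterion 7 and its copy in SAP Section 5.2, replace the 14-day minimum with *at least 4 months after the end of treatment*. Leave the period and starting point in Section 13.14 as they are; its cross-reference will then be correct.

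Do not align the two by counting both from the last dose. That could shorten the period for a woman whose decision to discontinue comes after her last dose. If the starting point is spelled out, use the later of the last dose of either study drug and the decision to discontinue, so that nobody's period is reduced.

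The sponsor should confirm that 4 months is intended and check that the patient information agrees.

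The cost is one sentence in two places. Under Section 17.10 it needs a written amendment approved by the sponsor and investigators, and by the health authorities and ethics committee where required if it is judged substantial. The patient information changes only if the check finds a difference. Criterion 7 would state a longer period than it does now, but Section 13.14 already requires that period. Sample size, analysis sets and analyses do not change.

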10.3 Exclusion Criteria

Patients eligible for this study must not fulfill the following criteria:

1. Pregnant or lactating women,
2. Participation in another clinical trial with any investigational drug within 30 days prior to study enrollment,
3. Any prior medical treatment for CML including tyrosine kinase inhibitors (TKIs) with the exception of hydroxyurea,
4. Period of time since CML diagnosis longer than 6 months,
5. Hypersensitivity to the active substances or to any of the excipients of the bosutinib and/or atezolizumab formulations,
6. Major surgery or radiotherapy within 14 days of enrollment,
7. Known clinically significant liver disease, including active viral, alcoholic, or other hepatitis, cirrhosis, and inherited liver disease,
8. Concomitant use of or need for medications known to prolong the QT interval,

9. Concomitant use with strong CYP3A inhibitors (ketoconazole, itraconazole, clarithromycin), moderate CYP3A inhibitors (erythromycin, fluconazole, diltiazem), or strong CYP3A inducers (rifampin, carbamazepine, phenytoin),
10. History of clinically significant or uncontrolled cardiac disease, including:
 - a. Stage II to IV congestive heart failure (CHF) as determined by the New York Heart Association (NYHA) classification system for heart failure,
 - b. Myocardial infarction within the previous 6 months,
 - c. Symptomatic cardiac arrhythmia requiring treatment,
 - d. Diagnosed or suspected congenital or acquired prolonged QT history or prolonged QTc. (QTcF should not exceed 500 msec.),
11. Grade III or IV fluid retention,
12. Uncontrolled hypomagnesemia or uncorrected symptomatic hypokalemia, due to potential effects on the QT interval,
13. Uncontrolled or symptomatic hypercalcemia,
14. Recent or ongoing clinically significant gastrointestinal (GI) disorder e.g. Crohn's Disease, Ulcerative Colitis or prior total or partial gastrectomy,
15. Autoimmune or infectious active disease that require treatment,
16. CML patient not in chronic phase at diagnosis,
17. Patients with known atypical transcript. An atypical transcript is defined by the presence of any transcript in the absence of the major transcripts b3a2 (e14a2) and b2a2 (e13a2) or p210 protein,
18. Patients with known resistant mutation(s) (T315I, E255K/V, Y253H, F359C/V). It is not necessary to perform mutation tests on the patient to be included in the study if they were not previously performed,
19. Individuals with an active malignancy,
20. Known seropositivity to human immunodeficiency virus (HIV), current acute or chronic hepatitis B (hepatitis B surface-antigen positive) and/or hepatitis C,
21. Any other disease, metabolic dysfunction, physical examination finding, or clinical laboratory finding that contraindicates the use of an investigational drug,
22. Patients with severe renal impairment.

11 TREATMENT

11.1 Study Treatment

Study treatments: Bosutinib (400 mg/day orally)

Atezolizumab (840 mg q2wk or 1680 mg q4wk)

Study drugs: Bosutinib (Bosulif® 100 mg film-coated tablets, Pfizer S.L.U.)

Yellow oval (width: 5.6 mm; length: 10.7 mm) biconvex, film-coated tablet debossed with “Pfizer” on one side and “100” on the other side. Each tablet contains 100 mg bosutinib (as monohydrate).

Bosutinib (Bosulif® 400 mg film-coated tablets, Pfizer S.L.U.)

Orange oval (width: 8.8 mm; length: 16.9 mm) biconvex, film-coated tablet debossed with “Pfizer” on one side and “400” on the other side. Each tablet contains 400 mg bosutinib (as monohydrate).

Atezolizumab (Tecentriq 840 mg concentrate for solution for infusion, Roche Registration GmbH)

Bosutinib study drug will be provided by Pfizer Europe MA EEIG and Atezolizumab will be provided by Roche Registration GmbH.

Patients will receive bosutinib at 400 mg/day orally. Bosutinib will be self-administered by the patient on a daily schedule.

Atezolizumab should be given intravenously in the site. If the first infusion is tolerated (intravenously administration over 60 minutes), all subsequent infusions may be delivered over 30 minutes. Patients will receive atezolizumab 840 mg q2w or 1680 mg q4w. Each 28-days (4 weeks) is referred to as 1 cycle.

Study treatments will be provided only to eligible patients at qualified centers.

